4.2 Primary Study Endpoints

- Ultrasound evaluation of the proximal humerus will aim at identifying 6 anatomical landmarks for PIHOVA with ultrasound:
 1. The humeral shaft,
 2. The surgical neck of the humerus,
 3. The lesser tubercle,
 4. The greater tubercle,
 5. The intertubercular sulcus
 6. The target site in the greater tubercle for needle insertion.

Each arm will receive a score that ranges from zero to six out of six depending on how many landmarks were identified successfully.

4.3 Secondary Study Endpoints

- Time used to identify all 6 anatomical landmarks using ultrasound in seconds.
- Depth of each landmark from the skin using ultrasound in centimeters.
- Correlation between upper arm thickness and the depth of the anatomical structures.
- Correlation between BMI and the depth of the anatomical structures

5 Subject Selection and Withdrawal

5.1 Inclusion Criteria

1- Males or females, 18 years of age or older.

2- BMI ≥ 18.5

5.2 Exclusion Criteria

1. Limited mobility/ range of motion of any of the upper extremities.
2. Prior surgical intervention on shoulder or humerus in any of the upper extremities.
3. History of arm dislocation with internal rotation in any of the upper extremities.
4. History of arm fracture in any of the upper extremities.
5. BMI in ranges: 25.1 – 29.9, 35.1 – 39.9

5.3 Subject Recruitment and Screening

Participants will be selected after chart review of current patients undergoing general, cardiac, thoracic, or vascular surgery. Patients will be approached in the preoperative clinic or during their hospitalization (preoperatively or postoperatively). Informed consent will be obtained on the same day of performing the ultrasound exam.

Participants will be separated into 3 cohorts based on BMI. The number of participants in each cohort is as follows: 10 patients with BMI 18.5 – 25 kg/m²; 10 patients with BMI 30-35 kg/m², 10 patients with BMI ≥ 40 kg/m².

6 Statistical methods

We will summarize the study population on baseline characteristics using appropriate summary statistics (e.g., mean \pm standard deviation, median [Q1, Q3], or N (%)).

6.1 Primary Analysis

We will summarize the success of landmark identification overall and by BMI category. Landmark identification is considered successful if all 6 landmarks are identified correctly. We will estimate the incidence of correct identification of all landmarks with a 95% bootstrap confidence interval. We will use bootstrap confidence intervals instead of binomial confidence intervals to account for intra-subject correlation because landmark identification will be performed twice per subject.

We will also report the median [Q1, Q3] of the mean number of landmarks identified correctly per patient overall and by BMI category. Results will be presented in tables and appropriate graphs. Descriptively, we will summarize the percent of correct identification by landmark location.

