Exclusion Criteria	
 1. Limited mobility/ range of motion of arms 2. Prior surgical intervention on shoulder or humerus 3. History of arm dislocation with internal rotation 4. History of arm fracture 5. BMI in ranges: 25.1 – 29.9, 35.1 – 39.9
Expected Sample Size	30 Patients (60 exams)
Statistical Methodology	We will summarize the total number of correctly identified landmarks per patient overall and by BMI category. We will also estimate the incidence of correctly identifying all landmarks per patient with a 95% bootstrap confidence interval.

List of Abbreviations

Abbreviation	Definition
BMI	Body Mass Index
CFD	Color Flow Doppler
CV	Central Venous
IO	Intraosseous
PH	Proximal Humerus
PHIO	Proximal Humerus Intraosseous
PHIOVA	Proximal Humerus Intraosseous Vascular Access
PIV	Peripheral Intravenous

1 Introduction

This document is a protocol for a human research study. This study is to be conducted according to US and international standards of Good Clinical Practice (FDA Title 21 and International Conference on Harmonization guidelines), applicable government regulations and Cleveland Clinic research policies and procedures.

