1.2 Clinical Data to Date

Ultrasound identification of proximal humeral structures is a novel concept with no current case reports or clinical trials demonstrating its use in clinical practice.

A correspondence letter by Bustamante et al.[8] demonstrated the use of ultrasound to identify PH structures on a cadaver model. Structures identified were the greater and lesser tubercles, intertubercular groove and surgical neck. Identification of these structures are necessary for PHIO needle placement. A 13-6 MHz ultrasound linear probe (SonoSite Inc; Bothell, Washington, USA) was used to identify these structures on 5 cadavers with body max indexes (BMI) ranging from 20 – 35. All structures were relatively superficial, within 3cm from the skin. Once landmarks and target site were identified, an IO needle was inserted and placement was confirmed with color flow doppler (CFD).

Failure to identify proximal humeral structures is considered an absolute contraindication to attempting PHIO placement. Prominent deltoid musculature and adipose tissue overlying proximal humeral landmarks can make identifying proximal humeral structures by palpation difficult if not impossible. As failed PHIO access of one arm precludes the use of the same arm for subsequent trials the first attempt must be optimized to allow for the greatest chance for success. If ultrasound is found to successfully identify all landmarks, even in patients with higher BMI's, failure to identify landmarks by palpation will no longer be considered an absolute contraindication.

2 Objectives

2.1 Primary Objectives:

Estimate the ability to successfully identify each of the six proximal humerus anatomical landmarks required for proximal humerus interosseous vascular access (PHIOVA), using ultrasound in patients with different body habitus: BMI 18.5-25 kg/m², BMI 30-35 kg/m², and BMI > 40 kg/m².

2.2 Secondary Objectives:

- Estimate the time used (in seconds) to identify all 6 anatomical landmarks using ultrasound in patients with different body habitus.
- Estimate the depth of each landmark (in centimeters) from the skin using ultrasound in patients with different body habitus.
- Estimate the correlation between upper arm thickness and the depth of the anatomical structures.
- Estimate the correlation between BMI and the depth of the anatomical structures.

3 Primary hypothesis

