We will test the hypothesis that all 6 anatomical landmarks for proximal humerus interosseous venous access can be identified using ultrasound in all patients irrespective of their BMI, or mid upper arm circumference.

4 Study Design

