6.2 Sample Size Considerations

We will enroll 30 patients, with 10 patients in each BMI category: BMI 18.5-25 kg/m², BMI 30-35 kg/m², and BMI > 40 kg/m². Given that investigators will be highly trained, we conservatively assume all landmarks will be identified 80% of the time. We expect very weak intra-subject correlation. Ignoring intra-subject correlation, we expect 95% confidence interval widths as small as 0.22 for overall incidence of correct identification and 0.38 within each BMI category. Confidence intervals will be somewhat larger depending on the strength of intra-subject correlation. Confidence interval widths will be narrower if investigators are more than 80% successful at identifying landmarks.

Study enrollment will start with 3 pilot patients with different BMI, but they will not be included in the statistical analysis. Thereby, a total of 33 patients will be enrolled in our study

References

1. Anson, J.A., *Vascular Access in Resuscitation. Is There a Role for the Intraosseous Route?* Anesthesiology, April 2014. **120**(4): p. 1015-31.
2. Paxton JH, K.T., Klausner HA *Proximal Humerus Intraosseous Infusion: A Preferred Emergency Venous Access.* The Journal of Trauma, September 2009. **67**(3): p. 606-11.
3. Eisen LA, N.M., Berger JS et al., *Mechanical complications of central venous catheters.* Journal of Intensive Care Mericine, 2006. **21**(40).
4. VonHoff DD., K.J., Burris HA. III, Miller LJ., *Does intraosseous equal intravenous? A pharmacokinetic study.* American Journal of Emergency Medicine, 2008. **26**: p. 31-8.
7. Kovar J, G.L., *Alternate route: the humerus bone – a viable option for IO access.* Journal of Emergency Medical Services, August 2010. **35**(8): p. 52-9.
8. Bustamante S, C.S., *Ultrasound to Improve Target Site Identification for Proximal Humerus Intraosseous Vascular Access.* In press Anesth Analg, 2016.

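### If every exam in a 10-patient BMI group succeeds, the planned 95% bootstrap interval is 100% to 100% or undefined, and the plan gives no fallback.

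*Combined protocol and SAP*

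**What the plan says.** Section 6.1 counts an exam as successful when all six landmarks are identified. It then says "We will estimate the incidence of correct identification of all landmarks with a 95% bootstrap confidence interval", and gives the reason: "We will use bootstrap confidence intervals instead of binomial confidence intervals to account for intra-subject correlation". The Study Summary repeats the method: "We will also estimate the incidence of correctly identifying all landmarks per patient with a 95% bootstrap confidence interval". Neither place names the type of bootstrap or the resampling unit, and neither says what is reported if every exam succeeds.

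The interval sentence in 6.1 does not itself mention BMI groups. The sentence that opens the paragraph does ("We will summarize the success of landmark identification overall and by BMI category"), and Sample Size Considerations settles the matter: "we expect 95% confidence interval widths as small as 0.22 for overall incidence of correct identification and 0.38 within each BMI category". Enrolment is planned "with 10 patients in each BMI category", and each patient is examined on both sides, so a group contributes 20 exams and the whole study 60.

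The hypothesis in Section 3 is that "all 6 anatomical landmarks for proximal humerus interosseous venous access can be identified using ultrasound in all patients". Sample Size Considerations assumes 80% success and calls this conservative. It expects only very weak correlation between a patient's two arms, and notes that intervals narrow above 80%. It does not say that the bootstrap width can reach zero.

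**The concern.** The interval method fails at the result the study hopes to see. With no failures in the data, every resample is also free of failures, so the bootstrap has no variation from which to form an interval. A BMI group with 20 successes in 20 exams would be reported as 100% with no uncertainty, or with no interval at all.

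The higher-BMI groups matter most. Section 1.2 says that if ultrasound identifies all landmarks, even at higher BMI, then "failure to identify landmarks by palpation will no longer be considered an absolute contraindication". Each higher-BMI group has 10 patients. An interval of 100% to 100% from 10 patients would suggest certainty that the data cannot give.

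**Working it through.** **The plan's own figures.** At 80% success the expected counts are 48/60 overall and 16/20 per group. Clopper-Pearson 95% limits from beta quantiles are 0.677 to 0.892 (width 0.2155) and 0.563 to 0.943 (width 0.3793). These match the stated 0.22 and 0.38. Wald (0.202, 0.351) and Wilson (0.200, 0.335) match neither figure. The stated widths are therefore exact binomial widths on exams and not bootstrap widths, so they do not reveal the boundary problem.

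**Bootstrap on 20/20.** With 10 patients and all 20 exams successful, 10,000 patient-level resamples all equal 1.0, so the bootstrap standard error is 0. Percentile and basic intervals are 1.0 to 1.0, and BCa returns no value. A bootstrap-t interval would be 0/0 (by reasoning, not run). Resampling exams instead of patients changes nothing.

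**Exact limits for the same data.** When all n units succeed, the lower limit is 0.025^(1/n).
- Group: n = 20 exams gives 83.2%; n = 10 patients (arms fully correlated) gives 69.2%.
- Overall: n = 60 gives 94.0%; n = 30 gives 88.4%.

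**Chance of collapse.** Let p be the true success rate and ICC the intra-subject correlation. The documents give only p = 80% and no ICC, so the other values are assumptions. Both arms of a patient succeed with probability p² + ICC·p(1−p), and all 10 patients do so with probability c = [p² + ICC·p(1−p)]^10. For at least one of three groups with the same rate, the chance is 1 − (1 − c)³.

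| True success | c, ICC 0 | c, ICC 0.5 | At least one of three groups |
|---|---|---|---|
| 80% | 0.64^10 = 1.2% | 0.72^10 = 3.7% | 3-11% |
| 90% | 0.81^10 = 12.2% | 0.855^10 = 20.9% | 32-50% |
| 95% | 0.9025^10 = 35.8% | 0.92625^10 = 46.5% | 74-85% |
| 98% | 0.9604^10 = 66.8% | 0.9702^10 = 73.9% | 96-98% |

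For the overall interval the chance is c³. At ICC 0 to 0.1 this is under 0.001% at 80%, 0.2-0.3% at 90%, about 5% at 95% and 30-32% at 98%.

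**Coverage of the percentile bootstrap.** This comes from exact enumeration of all splits of 10 or 30 patients into two, one or no successful arms. The bootstrap distribution of each split was obtained by convolution.

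| True success | Group, ICC 0 / 0.1 | Overall, ICC 0 / 0.1 |
|---|---|---|
| 80% | 92 / 91% | 96 / 96% |
| 90% | 87 / 86% | 94 / 93% |
| 95% | 64 / 62% | 95 / 94% |
| 98% | 33 / 32% | 70 / 68% |

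At 95% and 98% nearly all the group-level misses are the collapsed intervals themselves: 1 − 0.358 = 64% and 1 − 0.668 = 33%.

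**Near-perfect results.** For 19/20 the percentile bootstrap gives 85.0% to 100%. Its lower limit is above the exact 83.2% for 20/20. A rule that switches to an exact interval only when every exam succeeds would make a perfect result look worse than one with a failure.

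**The case against.** The study is observational and aims at estimation. No threshold or decision rule uses the interval, and the statement in Section 1.2 is conditioned on landmarks being identified, not on a confidence limit. At the only success rate the plan states, collapse in a given group has a 1-4% chance. A reader who sees 100% from 20 exams would probably understand how little that is. All of this stands and limits the importance of the point. It does not remove it: the plan calls 80% conservative and hypothesises success in all patients, so the higher rates are plausible.

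The plan also had a sound reason for the bootstrap, since it adapts to the correlation actually observed. If the two arms were fully correlated, exact intervals on exams would cover worse overall than the bootstrap: 89.5% against 94.6% at 80% success, and 88.4% against 95.0% at 90%. In a group at 80% success the figures are 86.0% against 88.6%. This stands too, and it is why the overall bootstrap should stay.

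A reader might infer that the whole primary analysis is unsound and every bootstrap interval must be replaced. The overall coverage figures do not support that at 80-95% success with weak correlation. A reader might also infer that the planned widths are wrong. They reproduce, though as exact widths.

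**Conclusion.** The point holds, mainly for the BMI groups. As written, the method gives a zero-width or undefined interval for a group in which every exam succeeds, and it covers too little as success approaches 100%: 64% at a true rate of 95% and 33% at 98%, for a nominal 95%. The overall interval is acceptable at 80-95% success with an ICC of 0 to 0.1 (93-96% coverage) but covers only about 70% at 98%.

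The coverage figures assume a patient-level percentile bootstrap. The true rates above 80% and all ICC values are assumptions. The collapse itself needs neither assumption. That intervals are meant for each group is read from the planned 0.38 width, because the interval sentence in 6.1 does not say so. Point estimates, medians and per-landmark percentages are unaffected. This should be fixed before analysis, but it does not threaten the study.

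**What to change.** In Section 6.1 and the Study Summary:

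1. **Each BMI group.** Report a Clopper-Pearson interval on the 20 exams as the main interval, for every result and not only perfect ones. Report with it a Clopper-Pearson interval with patients as the unit, as the bound that allows for intra-subject correlation. This uses exams/2 and successes/2 in the beta-quantile form, which accepts half counts. For 20/20 the lower limits are 83.2% and 69.2%.
2. **Overall.** Keep the bootstrap, state that patients are resampled, and name its type. Always report the same two exact intervals beside it. For 60/60 their lower limits are 94.0% and 88.4%.
3. **Sample Size Considerations.** Keep 0.22 and 0.38, and add that they refer to the exact interval on exams.

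Do not build in a fixed ICC such as 0.1. The documents give no such value, and it leaves per-group coverage unchanged from plain Clopper-Pearson in all 16 scenarios tested.

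Data collection and sample size do not change. The cost is wider group intervals when correlation is weak: mean width at ICC 0 is 0.37 against 0.32 for the bootstrap at 80% success, and 0.24 against 0.13 at 95%. The patient-level bound is wider again; for 20/20 its width is 1 − 0.692 = 0.308, against 1 − 0.832 = 0.168 on exams. Coverage of the exam-level exact interval can fall to about 86% per group if the two arms are fully correlated. That is why the patient-level interval is reported too: it covered at least 97.8% in every scenario tested (80-98% success, ICC 0 to 1).

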6.2 Secondary Analyses

We will estimate the median [Q1, Q3] of the mean time in seconds to identify all landmarks using ultrasound overall per patient overall and by BMI category.

Depth of each landmark will be summarized overall and by BMI category using appropriate summary statistics (e.g., mean \pm standard deviation and median [Q1, Q3]).

We will estimate the correlations between the following measures using Pearson correlation with 95% confidence intervals:

- Arm thickness with depth of anatomical structures
- BMI with depth of anatomical structures

Arm thickness, depth of anatomical structures, and BMI are only measured once per patient so standard methods are applicable (i.e., no repeated measures).

6.2 Sample Size Considerations

We will enroll 30 patients, with 10 patients in each BMI category: BMI 18.5-25 kg/m², BMI 30-35 kg/m², and BMI > 40 kg/m². Given that investigators will be highly trained, we conservatively assume all landmarks will be identified 80% of the time. We expect very weak intra-subject correlation. Ignoring intra-subject correlation, we expect 95% confidence interval widths as small as 0.22 for overall incidence of correct identification and 0.38 within each BMI category. Confidence intervals will be somewhat larger depending on the strength of intra-subject correlation. Confidence interval widths will be narrower if investigators are more than 80% successful at identifying landmarks.

Study enrollment will start with 3 pilot patients with different BMI, but they will not be included in the statistical analysis. Thereby, a total of 33 patients will be enrolled in our study

References

1. Anson, J.A., *Vascular Access in Resuscitation. Is There a Role for the Intraosseous Route?* Anesthesiology, April 2014. **120**(4): p. 1015-31.
2. Paxton JH, K.T., Klausner HA *Proximal Humerus Intraosseous Infusion: A Preferred Emergency Venous Access.* The Journal of Trauma, September 2009. **67**(3): p. 606-11.
3. Eisen LA, N.M., Berger JS et al., *Mechanical complications of central venous catheters.* Journal of Intensive Care Mericine, 2006. **21**(40).
4. VonHoff DD., K.J., Burris HA. III, Miller LJ., *Does intraosseous equal intravenous? A pharmacokinetic study.* American Journal of Emergency Medicine, 2008. **26**: p. 31-8.
7. Kovar J, G.L., *Alternate route: the humerus bone – a viable option for IO access.* Journal of Emergency Medical Services, August 2010. **35**(8): p. 52-9.
8. Bustamante S, C.S., *Ultrasound to Improve Target Site Identification for Proximal Humerus Intraosseous Vascular Access.* In press Anesth Analg, 2016.

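### The expected interval widths (0.22 overall, 0.38 per BMI category) are binomial widths, while the plan calls for a bootstrap of unstated type that, if percentile, falls short of 95% coverage with 10 patients per category

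*Combined protocol and SAP*

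**What the plan says.** Section 6.1 (Primary Analysis) defines success as identification of all six landmarks and continues: "We will estimate the incidence of correct identification of all landmarks with a 95% bootstrap confidence interval". It gives the reason for the method: "We will use bootstrap confidence intervals instead of binomial confidence intervals to account for intra-subject correlation", because "landmark identification will be performed twice per subject". It does not say which bootstrap interval is meant (percentile, basic, BCa) or whether patients or exams are resampled.

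Section 6.2 (Sample Size Considerations) sets the size by precision: "We will enroll 30 patients, with 10 patients in each BMI category". Its assumed rate is stated as "we conservatively assume all landmarks will be identified 80% of the time". Setting intra-subject correlation aside, which it says openly, it reports: "we expect 95% confidence interval widths as small as 0.22 for overall incidence of correct identification and 0.38 within each BMI category". It adds: "Confidence intervals will be somewhat larger depending on the strength of intra-subject correlation". It expects that correlation to be very weak and says widths shrink if success exceeds 80%. It does not name the method behind 0.22 and 0.38.

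**The concern.** The only numerical justification for 30 patients describes a type of interval that section 6.1 sets aside. A reader would take 0.38 as the narrowest interval to expect in a BMI category at 80% success. A common form of the planned method would give shorter intervals, and in a group of 10 patients a shorter bootstrap interval can reflect lost coverage and not better precision.

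This matters most in the BMI categories, because the primary objective is stated across body habitus and the hypothesis is success irrespective of BMI. An interval labelled 95% that covers less often, or collapses to a point at 100%, would overstate what 10 patients can show.

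**Working it through.** **Inputs.** From the documents: 30 patients, 10 per category; two exams per patient, hence 60 exams overall and 20 per category; success rate 0.80; two-sided 95% level. Assumed, because the documents give no figure: intra-patient correlation r from 0 to 0.5, resampling of whole patients (implied by the reason given in 6.1), and percentile limits.

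**Step 1: the plan's own figures.** The Clopper-Pearson limits for x successes in n are the 2.5% point of Beta(x, n−x+1) and the 97.5% point of Beta(x+1, n−x).

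- 48/60: 0.677 to 0.892, width 0.2155, rounds to 0.22.
- 16/20: 0.563 to 0.943, width 0.3793, rounds to 0.38.

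Other binomial forms (overall / category): Wald, 2 × 1.96 × √(0.8 × 0.2/n), gives 0.202 / 0.351, and Wilson gives 0.200 / 0.335. Neither matches. Wilson with continuity correction (0.215 / 0.377) also rounds to 0.22 / 0.38. Exact binomial is therefore the natural match but not the only one. Both matches are binomial methods.

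**Step 2: patient-level percentile bootstrap.** For success rate p and correlation r, a patient has two, one or no successes with probabilities p² + rp(1−p), 2p(1−p)(1−r) and (1−p)² + rp(1−p). At p = 0.8 and r = 0 these are 0.64, 0.32 and 0.04. All possible samples of patients were enumerated, the resampling distribution was computed exactly for each, and width and coverage were averaged over samples. The lower coverage figure does not count a tie at a limit as covered; the higher one does. Ties matter because 0.80 is itself a possible value of the estimate (16/20).

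| Patients | True rate | r | Mean width | Coverage |
|---|---|---|---|---|
| 10 | 0.80 | 0 | 0.317 | 89.0-92.0% |
| 10 | 0.80 | 0.1 | 0.329 | 88.0-91.0% |
| 10 | 0.80 | 0.3 | 0.351 | 86.2-88.7% |
| 10 | 0.80 | 0.5 | 0.372 | 84.9-86.7% |
| 30 | 0.80 | 0 | 0.195 | 91-96% |
| 30 | 0.80 | 0.3 | 0.224 | 91-96% |
| 10 | 0.90 | 0 | 0.217 | 85-87% |
| 10 | 0.95 | 0 | 0.128 | 63-64% |

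In a category the mean width stays below 0.38 even at r = 0.5.

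**Step 3: all exams succeed.** Every resample then equals 100%, so any bootstrap type gives zero width. At r = 0 the probability is p²⁰: 0.80²⁰ = 1.2%, 0.90²⁰ = 12%, 0.95²⁰ = 36%. It rises with correlation.

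**Step 4: an alternative that keeps the clustering.** With two exams per patient the design effect is 1 + r, so the effective size is n* = exams/(1 + r). Estimate r by ANOVA: (MSB − MSW)/(MSB + MSW), truncated to 0-1. Put n* into the Wilson interval. When all exams agree, set n* to the number of patients. For 20/20 in a category the lower limit is then 10/(10 + 1.96²) = 10/13.84 = 0.72, in place of an interval of zero width.

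Mean widths at 80% for r = 0 to 0.5 are 0.20-0.24 overall and 0.34-0.38 per category. Category coverage is about 96-97% at a true 80%, 95-96% at 90% and 93-95% at 95%. A category at an assumed 60% would have mean width 0.40-0.45.

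**The case against.** The strongest reply is that nothing was miscalculated. Both widths reproduce, and they are labelled as ignoring correlation, the one condition under which the stated reason for avoiding binomial intervals falls away. A closed-form width is an ordinary planning approximation, and per category it errs on the wide side (0.38 against about 0.32). All of this stands. A reader might infer an arithmetic slip or an undersized study, and the documents support neither.

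A second reply is that the coverage shortfall belongs to percentile limits, which the plan never names. This also stands. BCa limits do better at 80%: simulations gave coverage of about 94-98% counting ties, but 87-95% not counting them, at correlation 0 to 0.3. BCa is not a full cure, since it fell to about 81-87% at a true 90% with ties counted, and it too has zero width when all exams succeed. The figures are also sensitive to the exact rate: at zero correlation, percentile coverage in a category was about 93% at 79% and 89% at 81%.

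Three further readings go too far. The zero-correlation width of about 0.32 should not be paired with coverage near 87%, which needs a correlation of roughly 0.2 or more, whereas the plan expects very weak correlation. The statement that intervals widen with correlation is right in direction; only its baseline belongs to another method. Calling 80% conservative is defensible against a hypothesis of success in all patients, and no passage gives ultrasound success by BMI.

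Finally, 6.1 does not say outright that a bootstrap interval is computed in each category. The per-category width in the sample size section implies it.

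**Conclusion.** The point holds as a mismatch between sections and an underspecified method. The expected widths come from a binomial method, and the analysis section plans a bootstrap without naming its type or resampling unit.

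Under patient resampling with percentile limits, a 10-patient category at 80% has mean width about 0.32-0.35 and coverage from 92% down to 86% for correlation 0 to 0.3. So 0.38 is not a lower bound and the 95% label is not met. For all 30 patients at 80% the effect is small: width about 0.20-0.22, coverage about 91-96%.

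The category problem worsens above 80%, the direction implied by calling that rate conservative. The zero-width interval when all 20 exams succeed does not depend on the bootstrap type. The percentile coverage figures do, and they rest on the assumed correlations. The sample size is unaffected.

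**What to change.** In section 6.1, for the overall and per-category rates, replace the bootstrap with a Wilson interval on the effective sample size: exams divided by the estimated design effect, with the ANOVA intra-patient correlation truncated to 0-1, and the number of patients as the effective size when all exams agree. State explicitly that the interval is also given within each BMI category.

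In Sample Size Considerations, name this method and restate the expected widths at 80% as about 0.20-0.24 overall and 0.34-0.38 per category for correlation 0-0.5. Add that a category at an assumed 60% would have width about 0.40-0.45. The description of 80% as conservative can stay.

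If the bootstrap is kept, the least that is needed is its type, a statement that patients are resampled, widths restated for that type, and a rule for a category in which every exam succeeds.

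The cost is wording in two paragraphs and a few lines of code. Reported category intervals will be somewhat wider than percentile bootstrap limits, on average 0.34 against 0.32 at 80% and zero correlation. Enrolment does not change.
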